3.3.2 Visit Window

3.3.2.1 Analysis Visit Windows

For the purpose of the statistical analysis, all parameters presented by visit are allocated to the analysis visit as reported in [Table 5](#) below. The allocation to visit windows is performed after the imputation of date of first and last doses of study treatment as in Section [3.3.1.6](#). Measurements not done or with missing or partially missing dates will not be imputed to any analysis visit.

The visit closest to the scheduled visit day will be mapped to the visit window, irrespective of whether it is scheduled and unscheduled. If there are multiple measurements in the same analysis visit window, they will all be mapped to the same analysis visit window and the one closest to the scheduled visit day will be included in the analysis.

Scheduled visits are defined in 1.2. Schedule of Activities section of the CSP.

A summary of the analysis visit windows for scheduled visits is provided in [Table 5](#).

Table 5 – Analysis Window of Scheduled Visits

Analysis visit	Targeted visit day	Analysis visit windows (days)
Screening	D -21 to D -1	Up to D -1
Day 1	D1	D1
Week 1	D8	D5-D11
Week 2	D15	D12-D18
Week 4	D29	D24-D34
Week 8	D57	D52-D62
Week 12	D85	D80-D90
Week 14	D99	D94-D104

Early discontinuation visits (EDV) are mapped based on their time of occurrence to scheduled or unscheduled visit windows, and are not automatically mapped to Visit 8 as presented in CSP Section 1.2. Schedule of Activities.

3.3.2.2 Special cases

More than one measurement falls in the same visit window:

- PK measurements are mapped to the nominal visits
- One measurement falls on the scheduled visit day: the measurement on the scheduled visit date is used.
- No measurements fall on the scheduled visit day:

The time-interval between the scheduled visit day and the day of the measurement is to be considered.

- Different intervals: the nearest to the scheduled visit day is taken.
- Same intervals: the first measurement after the scheduled visit day is to be considered.
- Several measurements are collected during the same day the following is taken into consideration:
 - PK: selected timepoint within the day.
 - Numeric values: the average of measurement values.
 - Categorical values: clinically worst value.

3.3.2.3 Handling of Unscheduled Visits

Both unscheduled and scheduled visits are considered when assigning the visit windows as described in Section 3.3.2.1. If there are measurements that have not yet been assigned to an analysis window, they are labelled as described in [Table 6](#) below.

Table 6 – Analysis Windows for Unscheduled Visits

Analysis visit	Analysis visit windows (days)
(UNS) Week 0	D2-D4

(UNS) Week 3	D19-D23
(UNS) Week 5	D35-D39
(UNS) Week 6	D40-D46
(UNS) Week 7	D47-D51
(UNS) Week 9	D63-D67
(UNS) Week 10	D68-D74
(UNS) Week 11	D75-D79
(UNS) Week 13	D91-D93
(UNS) Week 15+	From D105

UNS= unscheduled visit

The unscheduled visits falling into the same window will be numbered sequentially with an increment of 0.1. For example, if two measurements are done in the unscheduled visit window that occur between visit Day 65 and Day 67, then these unscheduled visits will be numbered (UNS) Week 9.1 and (UNS) Week 9.2 in the order they occurred.

For measurements on a specific parameter that are not planned to be taken within a scheduled visit window according to the Schedule of Activities in the CSP but have been taken, a corresponding unscheduled visit will be created (e.g., An ApoA1 value measured at D8 will be mapped to (UNS) Week 1).

3.3.3 Multiplicity/Multiple Comparisons

Adjustment for multiple comparisons against placebo will be applied to the primary endpoint as listed in [Table 8](#). To strongly control the familywise error rate at the 0.05 level (2-sided) for the primary endpoint, a hierarchical testing strategy (closed testing procedure) will be employed. The alpha expenditure will be allocated to test the null hypotheses as detailed in [Table 7](#).

Table 7 – Order of Hierarchical Testing to Control Type I Error

Order	Null hypothesis	Alternative hypothesis
H1	$\mu_{AZD0780\ 30\ mg} = \mu_{placebo}$	$\mu_{AZD0780\ 30\ mg} \neq \mu_{placebo}$
H2	$\mu_{AZD0780\ 10\ mg} = \mu_{placebo}$	$\mu_{AZD0780\ 10\ mg} \neq \mu_{placebo}$
H3	$\mu_{AZD0780\ 3\ mg} = \mu_{placebo}$	$\mu_{AZD0780\ 3\ mg} \neq \mu_{placebo}$

H4	$\mu_{AZD0780\ 1\ mg} = \mu_{placebo}$	$\mu_{AZD0780\ 1\ mg} \neq \mu_{placebo}$
----	--	---

Where μ denotes the mean percent change from baseline of LDL-C at Week 12.

H1 will be tested first using the full test mass alpha. If H1 is rejected, then the full test mass will be recycled to test H2. If H2 is rejected, then H3 will be tested with full alpha, and if H3 is rejected, H4 will be further tested with full alpha. For all other comparisons, no multiplicity adjustment will be applied.

3.3.4 Handling of Protocol Deviations in Study Analysis

Important Protocol Deviations are detailed in the current, approved Protocol Deviation Plan.

Categories of IPDs:

1. Inclusion Criteria Deviations
2. Exclusion Criteria Deviations
3. Discontinuation Criteria for study product met but participant not withdrawn from study treatment
4. Discontinuation Criteria for overall study withdrawal met but participant not withdrawn from study
5. Investigational Product (IP) Deviation
6. Excluded Medications taken
7. Deviations related to study procedure
8. Other Important Protocol Deviations

IPDs will not be used to exclude any participant from any analysis set described in this SAP, unless otherwise specified. Please refer to Section 3.3.1.4 for definition of ICEs and the associated handling strategies. A list of all protocol deviations will be reviewed and documented by the study team physician, clinical pharmacology scientist (if relevant) and statistician prior to clinical data lock.

4 STATISTICAL ANALYSIS

This section provides information on definitions, derivations and analysis/data presentation per domain.

4.1 Study Population

The domain study population covers subject disposition, analysis sets, protocol deviations, demographics, baseline characteristics, disease characteristics, medical history, prior and concomitant medication, and study treatment compliance.

4.1.1 Subject Disposition and Completion Status

4.1.1.1 Definitions and Derivations

For disposition and completion status, the following definitions will apply:

- Subjects enrolled will be defined as a subject who signed the informed consent of the study.
- Subjects not randomised have consented to participate in the clinical study but are not subsequently randomly assigned to study intervention.
- Subjects randomised will be defined as a subject who has been randomised to a treatment group.
- Subjects randomised, not treated will be defined as a randomised subject who has not received any study treatment.
- Subjects who started treatment will be defined as a randomised subject who has received at least one dose of study treatment.
- Subjects who completed treatment will be defined as a subject who started treatment and has not permanently prematurely discontinued study treatment during the study. A subject who dies during participation without having permanently discontinued study treatment prior to date of death, will be considered to have completed treatment.
- Subjects who discontinued treatment will be defined as a subject who started treatment and has permanently prematurely discontinued study treatment for reasons other than death. The reasons for discontinuation as collected on the EOT eCRF will be presented. For reason collected as other, the specify field will be presented in listings but not in the disposition table.
- Subjects who completed study will be defined as a subject who has not withdrawn consent, has not been lost to follow-up and has not died.
- Subjects withdrawn from study will be defined as a subject who has withdrawn consent, has been lost to follow-up or died. The numbers for each of these categories will be presented.
- Subjects who discontinued treatment due to global/country situation, if applicable.
- Subjects who withdraw from study due to global/country situation, if applicable.

4.1.1.2 Presentation

Subject disposition and study completion status will be summarised overall and by planned treatment group (if applicable) for all enrolled subjects. Number of participants in each category will be presented, when applicable, percentages will also be presented. Disposition of enrolled participants will be presented in a listing, alongside age, sex assigned at birth, ethnicity, and race.

Participant recruitment will be summarized by region, country, and site. Region is defined in Appendix B (Section [7.2](#))

In case of global and local *vis major* events, number and percentage of affected participants in the randomized population will be summarized overall and by treatment group as defined in Section [3.3](#).

4.1.2 Analysis Sets

4.1.2.1 Definitions and Derivations

Analysis sets are defined in Section [3.2](#).

4.1.2.2 Presentation

Analysis sets will be presented by number and percentage (if applicable) of participants in each analysis set defined in Section [3.2](#), by treatment group and overall. The reason for exclusion from an analysis set will be tabulated and listed.

4.1.3 Protocol Deviations

4.1.3.1 Definitions and Derivations

Deviations from the protocol will be assessed as important or non-important by blinded members of the study team before clinical data lock and unblinding based on the latest approved version of the Protocol Deviation Plan.

4.1.3.2 Presentation

Important Protocol Deviations (IPDs) will be summarized for the FAS. Number and percentage of participants with at least one IPD in any of the IPD categories, as well as by category, will be presented by treatment group and overall.

Details about the IPDs, start and end date of the IPDs will be listed by participant.

4.1.4 Demographics

4.1.4.1 Definitions and Derivations

Demographic based on the FAS characteristics includes:

- Age (years)
- Age group (< 65, \geq 65 years)
- Sex (male, female)
- Race (Black or African American, Native Hawaiian or other Pacific Islander, American Indian or Alaska Native, Asian, White, Multiple, Other)
- Ethnicity (Hispanic or Latino, not Hispanic or Latino)
- Region and country

4.1.4.2 Presentation

Demographics will be summarised for participants in the FAS, by treatment group and overall.

Age will be presented as a continuous variable with descriptive statistics and categorically by age group. Sex, race, ethnicity, and region and country will be presented as categorical variables.

4.1.5 Baseline Characteristics

4.1.5.1 Definitions and Derivations

Baseline participant characteristics includes:

- Weight (kg)
- Height (cm)
- BMI (kg/m²)
- BMI group:
 - underweight (< 18.5 kg/m²),
 - normal weight (\geq 18.5 kg/m² and $<$ 25 kg/m²),
 - overweight (\geq 25 kg/m² and $<$ 30 kg/m²) and
 - obese (\geq 30 kg/m²).

BMI will be automatically calculated in the EDC as weight (kg)/[height (m)]² based on weight and height of the participant collected at baseline.

4.1.5.2 Presentation

Baseline participant characteristics will be presented descriptively for each treatment group and overall for the FAS. Height, weight, and BMI will be presented as continuous variables with descriptive statistics. BMI will also be presented categorically by BMI group.

4.1.6 Disease Characteristics

4.1.6.1 Definitions and Derivations

The following disease characteristics will be presented:

- Background lipid lowering statin therapy at baseline
- Non-prohibited background lipid lowering non-statin therapy at baseline
- The following parameters (from blood sample) at baseline:
 - Direct LDL-C
 - LDL-C (Friedewald method)
 - Total cholesterol
 - HDL-C
 - Triglycerides
 - Non-HDL-C
 - VLDL-C
 - ApoA1
 - ApoB
 - Lp(a)
 - Remnant cholesterol
 - hsCRP
 - PCSK9
- Renal function based on eGFR at screening
 - $45 \leq \text{eGFR} < 60$
 - $60 \leq \text{eGFR} < 90$
 - $\text{eGFR} \geq 90$
- Glycaemic control at baseline
 - HbA1c

4.1.6.2 Presentation

Disease characteristics will be summarised for each treatment group and overall for the FAS.

Background therapy and renal function based on eGFR will be characterized by categorical summary, and blood and glycaemic control parameters will be presented as continuous variables with descriptive statistics as defined in Section 3.3.1.

4.1.7 Medical History and Concomitant Disease

4.1.7.1 Definitions and Derivations

Medical history will be coded according to MedDRA version 26.0 or higher.

4.1.7.2 Presentation

Categorical summary of medical history will be presented in summary tables as number and percentages of participants by System Organ Class (SOC) and Preferred Term (PT) for each treatment group and overall for the FAS. Participants are only counted once per SOC and PT regardless of the number of occurrences within each category. Participants with events in more than one SOC/PT will be counted once in each of those SOC/PT. PT will be presented nested within the relevant SOC and sorted by international order of SOC and alphabetically by PT.

Medical history will be presented overall and by the age groups specified in Section 4.1.4.

4.1.8 Prior and Concomitant Medications

4.1.8.1 Definitions and Derivations

Prior medications are those taken prior to study treatment with a stop date prior to the first dose of the study treatment.

Concomitant medications (CM) are either ongoing or those with a stop date on or after the date of the first dose of study treatment, and must have started prior to or during treatment so there is at least one day in common with the study treatment.

Prohibited concomitant medications are defined in Section 5. and 6.9 of the CSP, and are listed in the latest approved version of the Prohibited Medication Memo. All other concomitant medications are classified as allowed.

Prior and concomitant medications will be coded according to WHODrug.

4.1.8.2 Presentation

Categorical summary of prior and concomitant medications will be presented.

Prior and concomitant medications will be summarized by ATC classification and generic drug name for each treatment group and overall for the FAS. Participants are only counted once per ATC classification and generic drug name regardless of the number of medications

within each category. Generic drug name will be presented nested within the relevant ATC classification and sorted alphabetically by ATC classification and then generic drug name.

Prior medications, disallowed concomitant medications, and allowed concomitant medications will be presented separately.

4.1.9 Study Drug Compliance

4.1.9.1 Definitions and Derivations

Percent compliance to treatment will be calculated for each participant based on tablet count as: the number of tablets taken (dispensed minus returned), divided by the number of tablets expected to have been taken, multiplied by one hundred. The number of tablets expected to have been taken is defined as 1 tablet/bottle (3 tablets in total) multiplied by ‘date of last dose minus date of first dose plus one’. If the number of tablets dispensed, or the number of tablets returned, is missing for at least one observation for a participant, compliance is not calculated for that participant.

4.1.9.2 Presentation

Compliance (%) will be summarised as a continuous and categorical variable for each treatment group and overall for the FAS.

The compliance categories to be presented are the following:

1. <80% compliance
2. 80%-120% compliance
3. >120% compliance

4.2 Endpoint Analyses

This section covers details related to the endpoint analyses such as primary, secondary, exploratory including sensitivity and supportive analyses.

Table 8 - Objectives, Endpoints and Estimand attributes

Statistical category	Endpoint	Population	Intercurrent event strategy	Population level summary (analysis)	Details in section
Objective 1: To evaluate the effect of different doses of AZD0780 on LDL-C versus placebo in “ideal” scenarios in which intercurrent events would not occur					
Primary analysis of	Percent change from baseline of direct LDL-C at Week 12	FAS	See details in Table 3 .	Difference in mean percent change from	4.2.1

Statistical category	Endpoint	Population	Intercurrent event strategy	Population level summary (analysis)	Details in section
the primary endpoint				baseline to Week 12 between treatment groups (LSMD from MMRM model without explicit imputation).	
Objective 2a: To evaluate the effect of different doses of AZD0780 on LDL-C versus placebo in “real-world” conditions					
Primary analysis of the secondary endpoint	Percent change from baseline of direct LDL-C at Week 12	FAS	See details in Table 3 .	Difference in mean percent change from baseline to Week 12 between treatment groups (LSMD from MMRM model with multiple imputation).	4.2.2
Objective 2b: To assess the PK of AZD0780					
Primary analysis of the secondary endpoint	AZD0780 plasma concentrations summarized by sampling timepoints	PK analysis set		Summary statistics presented by sampling timepoints.	4.4
Objective 2c: To evaluate the effects of AZD0780 on other lipid parameters and inflammatory markers versus placebo in “ideal” scenarios in which intercurrent events would not occur					
Primary analysis of the secondary endpoint	Percent change from baseline at Week 12 in: 
 • Total cholesterol • HDL-C • Triglycerides 	FAS	See details in Table 3 .	Difference in mean percent change from baseline to Week 12 between treatment groups (LSMD from	4.2.3

Statistical category	Endpoint	Population	Intercurrent event strategy	Population level summary (analysis)	Details in section
	
 • Non-HDL-C • VLDL-C • ApoA1 • ApoB • Lp(a) • Remnant cholesterol • hsCRP 			MMRM model without explicit imputation).	
Objective 2d: To evaluate the effects of AZD0780 on other lipid parameters and inflammatory markers versus placebo in “real-world” conditions					
Primary analysis of the secondary endpoint	Percent change from baseline at Week 12 in: 
 • Total cholesterol • HDL-C • Triglycerides • Non-HDL-C • VLDL-C • ApoA1 • ApoB • Lp(a) • Remnant cholesterol • hsCRP 	FAS	See details in Table 3 .	Difference in mean percent change from baseline to Week 12 between treatment groups (LSMD from MMRM model with multiple imputation).	4.2.4
Objective 3: To assess the safety and tolerability of AZD0780					
Safety and tolerability	Safety and tolerability will be assessed in terms of AEs, vital signs, ECG, and clinical laboratory evaluations	SAS	See details in Table 3 .	Descriptive statistics	4.6.2 4.6.3 4.6.4 4.6.5 4.6.6
Objective 4: Exploratory objectives					
Exploratory analysis	To assess baseline PCSK9 levels	NA	NA	NA	Results of baseline PCSK9

Statistical category	Endpoint	Population	Intercurrent event strategy	Population level summary (analysis)	Details in section
					levels may be reported outside of the CSR.
Exploratory analysis	To collect and store plasma, serum, and urine samples for potential future exploratory biomarkers involved in PK, PD, safety and tolerability related to AZD0780 treatment and/or cardiometabolic diseases	NA	NA	NA	Results of potential future exploratory biomarkers may be reported outside of the CSR
Exploratory analysis	Optional: To store DNA from blood samples according to each country's local and ethical procedures for future exploratory research into genetic variations that may influence AZD0780 treatment	NA	NA	NA	Results of possible future genetic research may be reported outside of the CSR

AE = adverse event; ApoA1 = apolipoprotein A-1; ApoB = apolipoprotein B-100; CSR = Clinical Study Report; DNA = Deoxyribonucleic acid; ECG = electrocardiogram; FAS = Full Analysis Set; HDL-C = high-density lipoprotein cholesterol; hsCRP = high-sensitivity C-reactive protein; LDL-C = low-density lipoprotein cholesterol; Lp(a) = lipoprotein (a); LSMD = Least Square Mean Difference; MMRM = Mixed Model for Repeated Measures; NA = Not Applicable; PCSK9 = Proprotein Convertase Subtilisin/Kexin Type 9; PD = Pharmacodynamic; PK = pharmacokinetic(s); SAS = Safety Analysis Set; VLDL-C = very-low-density lipoprotein cholesterol.

4.2.1 Primary Endpoint

4.2.1.1 Definition

The primary efficacy endpoint is percent change from baseline to Week 12 in direct LDL-C. The clinical question of interest is:

What is the difference in means of percent change in LDL-C from baseline to Week 12 in participants with dyslipidemia treated with AZD0780 vs placebo in the hypothetical condition that all participants could adhere to study intervention and non-prohibited

background lipid lowering statin and non-statin therapy, prohibited medications affecting lipid parameters were not available, regardless of whether additional treatment is used, where participants cannot die.

The primary estimand attributes are defined as:

- Treatment: AZD0780 or placebo.
- Population: Male and female participants of non-childbearing potential, 18 to 75 years of age with dyslipidemia, defined by the inclusion and exclusion criteria. Implemented using FAS.
- Endpoint: Percent change in direct LDL-C from baseline at Week 12.
- Population-level summary measure: Difference in means of percent change in direct LDL-C from baseline to Week 12 between AZD0780 and placebo.
- Handling of intercurrent event: The hypothetical strategy will be used for premature and permanent discontinuation of study treatment; change in background lipid lowering statin therapy; initiation, change or discontinuation in non-prohibited background lipid lowering non-statin therapy and intake of prohibited medications affecting lipid parameters. Efficacy assessments obtained after these will not be included in the analysis. Initiation or changes in other concomitant or prohibited medication will be handled with treatment policy strategy. Deaths will be handled with a hypothetical strategy.

4.2.1.2 Derivations

Direct LDL-C below the LLOQ for which the exact value cannot be determined, will be replaced with the LLOQ divided by the squared root of 2.

Percent change from baseline is derived as:

$$\frac{(y_{V_j} - y_{BL})}{y_{BL}} * 100$$

where

- y_{V_j} represents the efficacy measurement at Visit j , and
 - j refers to the visit number, specifically 3,4,5,6,7 (i.e., the visits included in the analysis),
 - In case of treatment discontinuation ICE, j includes all visits up to and including the date of treatment discontinuation.

- For every other ICE handled with the hypothetical strategy, j refers to the last visit before the first ICE occurrence handled with the hypothetical strategy, as detailed in Section 3.3.1.4.
- y_{BL} is the efficacy measurement at Baseline.

4.2.1.3 Handling of Dropouts and Missing Data

Missing baseline measurements

Missing baseline values will not be imputed.

Non-monotone missing data

Non-monotone missing data means that observations exist after the time point with the missing data.

Non-monotone missing data will not be explicitly imputed.

Monotone missing data

Monotone missing data are defined on a participant level as missing data that constitutes the end of participant follow-up.

Monotone missing data will be assumed to be Missing at Random (MAR) and will not be explicitly imputed.

4.2.1.4 Primary Analysis of Primary Endpoint

The summary measure for the primary endpoint will be the difference in least squares mean of percent change from baseline of direct LDL-C at Week 12. The primary endpoint will be analysed using a MMRM on the FAS. Percent change from baseline in direct LDL-C at each post-baseline visit will be used as the dependent variable. The model will include the fixed effects of baseline direct LDL-C, treatment group, visit, and treatment-by-visit interaction, and the random effect (random intercept) of participant. The Restricted Maximum Likelihood estimation approach will be used with a compound symmetry covariance structure for repeated measures.

In case of non-convergence, an ANCOVA model will be run. The model will include the fixed effects of baseline direct LDL-C and treatment group as covariates. In this model, the dependent variable will be the percent change in direct LDL-C from baseline to Week 12.

The results will be summarized by the difference in least squares means, 95% confidence interval, and p-value.

The hierarchical testing strategy will be employed to strongly control the familywise error rate at the 0.05 level (2-sided), as described in Section 3.3.3.

The primary endpoint will also be characterized by descriptive statistics (as defined in Section 3.3.1) at each scheduled visit and visualized with line plot.

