## **9.2 Sample Size Determination**

The study will randomize approximately 375 participants in order to have approximately 320 evaluable participants who complete the 12-week treatment period to support the evaluation of the primary endpoint (the discontinuation rate is assumed to be approximately 15%).

Participants will be randomized in a 1:1:1:1:1 manner to receive AZD0780 [ ] mg, [ ] mg, [ ] mg, [ ] mg, or corresponding placebo.

The sample size is driven by the objective to assess the safety and tolerability of AZD0780. The chosen sample size is believed to be sufficient for the creation of a robust safety database.

The sample size of approximately 64 evaluable participants who complete the 12-week treatment period in each arm will provide more than 90% power for the test of each dose of AZD0780 versus placebo to detect a difference of [ ] in percent change from baseline in LDL-C to Week 12. The calculations assume SD = [ ] and a 2-sided alpha level of 0.05, and are based on a t-test with normal approximation for percent change from baseline.

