1 INTRODUCTION

This study is designed to explore the efficacy, safety, tolerability, and pharmacokinetics (PK) across different dose levels of AZD0780, a small molecule PCSK9 inhibitor, administered orally for up to 12 weeks in participants with elevated LDL-C.

This is a randomized, multicenter, parallel-group, double-blind, placebo-controlled, dose-ranging, Phase IIb study in approximately 375 participants with dyslipidemia. The primary objective of the study is to investigate the effect of AZD0780 on LDL-C levels across different dose levels.

The screening period will be up to 3 weeks prior to randomization. Participants with a fasting LDL-C of ≥ 70 mg/dL and < 190 mg/dL, and triglycerides < 400 mg/dL at screening will be eligible. Eligible participants will attend 6 visits during the treatment period and one additional visit in the follow-up period. Eligible participants will be randomized across 5 different treatment groups in a 1:1:1:1:1 ratio for a 12-week treatment period. The planned treatments arms are AZD0780 1 mg, AZD0780 3 mg, AZD0780 10 mg, AZD0780 30 mg, and placebo.

Throughout the document and the subsequent statistical deliverables phrases “subject” and “participant” are used as synonyms and are interchangeable.

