3.3.1.2 Baseline

For analyses on the full analysis set (FAS) and the safety analysis set (SAS), baseline is defined as the last non-missing value prior to or on the date of study treatment administration including unscheduled assessments that occur prior to first administration of study treatment.

Baseline definition will consider date, and time of data collection (if available). The pre-dose assessment will be used as baseline. If time of first study treatment administration is unavailable, the measurement will be assumed to be pre-dose unless the CSP suggests otherwise. Additionally, if there is only one visit eligible to assess participant status at baseline and it occurs on the date of randomization without a recorded time for the assessment, we should also assume it is a baseline assessment unless the CSP suggests otherwise. If more than one assessment is conducted before the first study treatment

administration, assessment conducted closest to the first study treatment intake will be taken as the baseline value.

If there are more than one assessment that meet the baseline criteria (for example, several assessments on the same date prior to first administration and occurring either at the same time or one or all of them without collected time), the average of these values will be used as a baseline. In case of qualitative variables, the clinically least abnormal value will be taken as the baseline value.

Missing baseline values will not be imputed.

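### The LDL-C model makes no covariate use of the screening LDL-C held for every participant; adding it would narrow the intervals slightly

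*SAP*

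**What the plan says.** SAP 4.2.1.4 specifies the primary mixed model: "The model will include the fixed effects of baseline direct LDL-C, treatment group, visit, and treatment-by-visit interaction", with a participant random intercept and one compound-symmetry structure. The fallback ANCOVA keeps the same single lipid covariate. SAP 4.2.2.4 uses the same model for the treatment-policy analysis after imputation, and the subgroup analyses refit it.

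On baseline, SAP 3.3.1.2 says that when there are several pre-dose values the "assessment conducted closest to the first study treatment intake will be taken as the baseline value". Averaging is reserved for values that tie, such as several on one date. Baseline is therefore normally the Day 1 sample alone, and SAP 4.2.1.2 divides by that value to form the percent change.

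The Schedule of Activities (Protocol 1.2) marks LDL-C at both screening and Day 1, and Protocol 5.3.2 requires fasting at both. Eligibility rests on the screening value: "Participants with a fasting LDL-C of ≥ 70 mg/dL and < 190 mg/dL" (SAP 1). That value has two roles in the plan: the eligibility decision, and a fallback baseline if Day 1 is missing. No primary, sensitivity or supplementary model uses it as a covariate.

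**The concern.** Visit-to-visit variation in the Day 1 value enters the outcome twice, since that value is both subtracted and used as the divisor. Adjusting for Day 1 removes part of this. A second pre-treatment measurement carries further information on the person's usual level, and it has already been collected. It precedes randomisation, so adjusting for it cannot bias the comparison, and the estimand is unchanged as long as Day 1 stays the denominator.

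What is at stake is interval width. Protocol 4.3 wants to show that the highest dose adds little and that at least one dose does clearly less. Those are questions of estimation, for which precision matters even if every test against placebo succeeds. The possible interim analysis may rest on as few as 175 completers, or 175/5 = 35 per arm.

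**Working it through.** **1. The plan's own figures.** Protocol 9.2: "The study will randomize approximately 375 participants in order to have approximately 320 evaluable participants", with about 15% discontinuation. 375 × 0.85 = 318.75, and 75 × 0.85 = 63.75 per arm, which agrees with the stated 320 and 64. The power claim is that 64 per arm "will provide more than 90% power for the test of each dose of AZD0780 versus placebo to detect a difference of" a value that is redacted; the SD is redacted too. The sizing uses "a 2-sided alpha level of 0.05, and are based on a t-test with normal approximation for percent change from baseline". It therefore cannot be reproduced, but it can be inverted: 90% power at 64 per arm needs effect/SD = (1.960 + 1.282) × √(2/64) = 0.573. The claim holds for any ratio at or above that.

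**2. Direction of the gain.** Take screening, Day 1 and Week 12 values with equal pairwise correlation r. The residual variance of Week 12 is 1 − r² given Day 1 alone, and 1 − 2r²/(1 + r) given both. The ratio is (1 + 2r)/(1 + r)², which is below 1 for any r > 0. At r = 0.5 it is 0.89, and at r = 0.7 it is 2.4/2.89 = 0.83. These figures ignore variation in response between people and the entry range, both of which shrink the gain.

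**3. Size under the planned pooled-variance model.** Large-sample simulation of 100 × (Week 12/Day 1 − 1) in five arms, with common covariate slopes and one residual variance, fitted at Week 12.
- From the documents: the entry range of 70 to <190 mg/dL applied to the screening value, five arms, and equal allocation.
- Assumed: between-person SD 28 mg/dL; within-person CV 6%, 9% or 12%; response SD 15 points on placebo and 18 on active, or 10 in all arms; true reductions of 35% to 50% in the active arms; mean LDL-C 105 to 125 mg/dL, a choice that barely affects the results.
- The CI narrows by 1 − √(1 − fall). For example, 1 − √0.966 = 1.7%.

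| Assumption | Fall in pooled variance | CI narrower by | Fall with 8% extra screening noise |
|---|---|---|---|
| CV 9% (central) | 3.4% | 1.7% | 2.3% |
| CV 6% | 2.0% | 1.0% | 1.0% |
| CV 12% | 4.4% | 2.2% | 3.4% |
| CV 9%, response SD 10 | 7.5% | 3.8% | 5.2% |

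The last column covers a screening assay that differs from the endpoint assay.

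**4. Does a single-visit fit understate the gain?** A separate simulation with five post-baseline visits and compound symmetry gave variance ratios within 0.002 of the Week 12 ANCOVA. It covered a wider set of assumptions (visit-to-visit correlation 0.5 to 0.85, response SD 0 to 20 points). Variance fell in every scenario, by 2.5% to 17%. The top of that range needs no variation in response between people.

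**5. What it is worth.** If power were exactly 90%, variance falls of 2.0%, 3.4% and 7.5% would give about 90.6%, 91.0% and 92.1%. In participants, 375 × (1/0.966 − 1) is about 13 in the central case, 8 at CV 6% and 30 at response SD 10.

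**The case against.** The strongest case against is that nothing here is broken. Adjusting for one baseline value is valid. Protocol 9.2 says the trial is sized for safety and states more than 90% power per dose, and no test or dose decision can be shown to turn on a 2% narrower interval. That stands, and it limits the point to an optional improvement.

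A reader might infer a larger gain by working out each arm separately. In the central case the residual SD falls from 19.7 to 18.9 on placebo and from 19.7 to 19.4 in an active arm at −40%. The variance falls are 1 − (18.9/19.7)² = 8.0% and 1 − (19.4/19.7)² = 3.0%, averaging 5.5% for a pairwise contrast. SAP 4.2.1.4 does not support that reading. It specifies one covariance structure for all arms, so the reported intervals use a variance that four active arms dominate: (8.0 + 4 × 3.0)/5 = 4.0%, and common slopes bring it down to about 3.4%.

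The assay objection stands in part. The endpoint is direct LDL-C (SAP 4.2.1.1), whereas Protocol 4.1 describes a Friedewald calculation with reflex testing. The documents do not say that direct LDL-C is run at screening. A mismatch does not bias the comparison, but it costs precision, as the last column of the table shows.

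It is also fair to say that every variability input is assumed, and that the edit is more than one model term. Appendix A imputes from baseline and post-baseline values only, so changing the analysis model alone would leave the two inconsistent. Section 4.2.1.4 also serves ten other endpoints, and ApoB, ApoA1, Lp(a) and hsCRP have no screening sample.

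**Conclusion.** The point holds as a modest efficiency gain. The LDL-C model leaves unused a pre-randomisation measurement held for every participant. Using it would lower the pooled variance by about 2% to 7.5%, with about 3% as the central case and an interval about 2% narrower. With a noisier screening assay the gain is about 1% to 5%. These sizes rest on an assumed within-person CV of 6-12% and a response SD of 10-18 points; the direction does not. The gain shrinks as response varies more between people, because screening LDL-C cannot explain that part.

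A reader might infer that the planned analysis is wrong, that the trial is underpowered, or that the screening value is thrown away. The documents support none of these. The model is valid as written, more than 90% power is stated, and the screening value does decide eligibility and can serve as baseline. Nor is the change wholly free: it costs one degree of freedom, 1/314 or about 0.3% of the residual degrees of freedom in an ANCOVA on 320 (320 − 5 arms − 1 covariate), and more in small subgroups.

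**What to change.** Before unblinding:

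- In SAP 4.2.1.4, add screening (Visit 1) LDL-C as a continuous fixed covariate beside baseline direct LDL-C, in both the mixed model and the fallback ANCOVA. Carry it into 4.2.2.4 by reference. State that it applies to LDL-C only, so that the models for the other lipid and inflammatory endpoints are unchanged.
- Add the same covariate to the LDL-C imputation models in Appendix A, including the placebo-washout version.
- Keep Day 1 as the denominator for percent change.
- State which value counts as the screening LDL-C when a test is repeated or a participant is rescreened (Protocol 5.4), or when a routine-care result is accepted (Protocol 8). If a participant's baseline already is the screening value, use it for both terms.
- Record which assay was used at screening.

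The cost is a small SAP edit, the matching sentence in Protocol 9.4.2.1 at the next amendment, and one degree of freedom. No new data or visits are needed.
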